5.10 Missing data

We need to evaluate the quality control procedures in historical control dataset, with respect to missing data and outlying values. We expect that most variables that will enter the analyses will have few missing values. In cases for which more than one percent of the observations have missing values, we have used various approaches, all depending on the “missing at random” (MAR) assumption. If missingness can be considered to be random after conditioning on observed data, then the mechanism is said to be missing at random.⁴²⁻⁴⁴ Both mixed-effects models and multiple imputation are appropriate under these circumstances. When the missingness depends on the values of the missing data, however, the missing value mechanism is said to be non-ignorable, and standard statistical procedures are no longer valid. As discussed by Verbeke and Molenbergh, virtually all strategies for dealing with this type of data are based on a number of “untestable and unverifiable” assumptions, which limit their utility.⁴⁵ Clearly, the best defense is to simply avoid missing data as far as humanly possible.

Missing data patterns of both prospective subjects and historical controls will be assessed by age, and other appropriate characteristics.⁴⁶ Missing data patterns of the strategies will be compared to determine similarity. Analyses will be made comparing number of missing values of the prospective and historical control dataset. In this case, the outcome is dichotomous, missing or not missing, and the event rates of the two groups will be compared by Poisson regression, or negative binomial regression if the Poisson model is over-dispersed. This analysis will include covariates specified for the primary and alternative analyses. Similar to logistic regression, the exponentiated regression coefficients of the model are incident rate ratios, comparing event rates of the intervention vs. historical cohort groups.

6 Bias in the Hybrid Study

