5.3 Covariate Analyses

The prospective participants and historical controls in the study may differ in ways other than the interventions or exposures under investigation. Covariates will be used to adjust the regressions prespecified in the primary analysis for potential differences between the control and prospective arms, and in derivation of propensity scores used to adjust for biases between the two arms, either by weighting subjects in the alternative analysis or by matching subjects in exploratory analyses..

The following variables are candidates for inclusion as covariates in the primary analysis: regression with covariates. These baseline covariates are present before blood draw.

- Maternal age
- Categorical parity: multiparous vs. nulliparous
- Maternal substance use disorders assessed as Neonatal Opioid Withdrawal Syndrome

The following variables are candidates for inclusion as covariates in the alternative analysis using inverse probability score weighting, and in the exploratory analysis using propensity matching. These baseline covariates are present before blood draw.

- Maternal age
- Categorical parity (nulliparous vs. multiparous)
- Gravidity (integer)
- Number of term children
- Number of miscarriages
- Maternal race
- Pre-pregnancy continuous BMI
- Pre-pregnancy categorical low BMI<19
- Maternal height
- Maternal chronic hypertension
- Gestational diabetes
- Insurance status
- Smoking status
- Maternal substance use disorders assessed as Neonatal Opioid Withdrawal Syndrome
- Delivery outside of ChristianaCare

Inclusion of covariates in the covariate-adjusted primary, alternative and exploratory analyses will depend on the proportion of missing values for the covariate, as follows. For each candidate variable, if fewer than 1% of subjects have a missing value, that variable will be included as a covariate in the analysis. Sensitivity of results to missing data will be examined using missing data analysis methods.

The primary and alternative analyses will use cases with complete data for the included covariates, provided that no more than 5% of the total subjects are excluded from the analysis. If more than 5% of the total subjects would be excluded from the analysis,

candidate variables will be dropped from the analyses in order of the percent missing, until no more than 5% of the total subjects are excluded from the analysis.

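### The Section 5.10 comparison of missing data between arms adjusts for delivery outside ChristianaCare, which can pull the arm ratio toward 1 when crude losses differ

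*SAP*

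**What the plan says.** SAP Section 5.10 gives the purpose of the comparison: "Missing data patterns of the strategies will be compared to determine similarity". For the dichotomous outcome missing or not missing, "the event rates of the two groups will be compared by Poisson regression", with negative binomial regression as the fallback for over-dispersion. The exponentiated arm coefficient is read as a rate ratio. The adjustment set is stated without exception: "This analysis will include covariates specified for the primary and alternative analyses".

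Section 5.3 supplies that set. The list for the alternative analysis includes "Delivery outside of ChristianaCare". The lists for the primary and the alternative analysis both include "Maternal substance use disorders assessed as Neonatal Opioid Withdrawal Syndrome". Of each list the section says: "These baseline covariates are present before blood draw". That cannot be true of the place of delivery or of a diagnosis made in the newborn.

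Two other provisions matter. Section 5.1 admits to the mITT population, on which the primary analysis runs, only women with both co-primary outcomes known. The covariates of the primary analysis are maternal age, parity and NOWS, so that analysis does not adjust for delivery site.

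**The concern.** The question is whether the two arms lost similar proportions of women. A model that holds delivery site fixed answers a different one: whether missingness is similar among women who delivered in the same kind of place. If women who deliver elsewhere are harder to follow to neonatal discharge, and if they are commoner in the prospective arm, delivery site lies on the path from arm to missing outcome. Adjusting for it removes the part of the difference that the check should reveal.

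Unequal loss is plausible here. Prospective women are enrolled around 20 weeks, while controls are identified retrospectively from ChristianaCare's database. Because mITT membership needs both outcomes, unequal loss is a form of selection into the primary comparison. An adjusted ratio near 1 could then be taken as reassurance that the primary analysis, which leaves delivery site out, has not earned.

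**Working it through.** The SAP states no figure for this comparison, so there is none to reproduce. What follows is an illustration.

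**Inputs from the SAP (Section 4).** About 1,453 prospective women and 10,000 controls, 11,453 in all.

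**Assumed inputs (not in the SAP).** Outside delivery in 2%, 4% or 6% of prospective women and 0.2% of controls. Outcome missing in 80% of outside and 0.5% of inside deliveries, the same in both arms.

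**Step 1, crude comparison.** Proportion missing = o × 0.80 + (1 − o) × 0.005, where o is the proportion delivering outside.
- Controls: 0.002 × 0.80 + 0.998 × 0.005 = 0.00659.
- Prospective, o = 2%: 0.0160 + 0.0049 = 0.0209; ratio 0.0209 / 0.00659 = 3.2.
- Prospective, o = 4%: 0.0320 + 0.0048 = 0.0368; ratio 5.6.
- Prospective, o = 6%: 0.0480 + 0.0047 = 0.0527; ratio 8.0.

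**Step 2, adjusted for delivery site.** The arm ratio is 0.80 / 0.80 = 1 among outside deliveries and 0.005 / 0.005 = 1 among inside deliveries. The adjusted ratio is therefore 1.0 in all three settings.

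**Step 3, simulation at these arm sizes, two-sided 5%.** The crude difference is detected in 99-100% of replicates. With delivery site in an ordinary Poisson model the arm effect is detected in under 1%; with robust standard errors, in 5-8%, close to the nominal rate. Ordinary Poisson variance is too large by about 1 / (1 − p) for a yes/no outcome with probability p. That is negligible at p = 0.01 but a factor of 5 at p = 0.80. This is under-dispersion, so a switch triggered by over-dispersion does not address it.

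**Step 4, other assumed rates.** With outside delivery of 5-8% versus 0.4-2%, and outcomes missing in 80-90% of outside and 0.2-0.5% of inside deliveries, crude ratios are 3.3 to 8.5 and adjusted ratios again 1.00.

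**Step 5, loss by another route.** Let inside deliveries be missing in 2% of prospective women and 0.5% of controls, with the rest as in step 1. Crude ratios become (0.0160 + 0.0196) / 0.00659 = 5.4, (0.0320 + 0.0192) / 0.00659 = 7.8 and (0.0480 + 0.0188) / 0.00659 = 10.1. The adjusted ratio is about 2.4-2.5, detected in 96-98% of replicates. The model understates the crude difference but does not hide it.

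**Step 6, NOWS.** Deletion of women without a NOWS value does not by itself mask a difference. If losses are 5% versus 1% and a share q of lost women lacks NOWS in both arms, the complete-case ratio is [0.05(1 − q) / (1 − 0.05q)] / [0.01(1 − q) / (1 − 0.01q)]. At q = 0.9 this is 0.00524 / 0.00101 = 5.2, against 5.0 before deletion. Masking needs the lack of NOWS to be concentrated among lost prospective women.

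**The case against.** The strongest reply is that the adjusted ratio of 1.0 is built into the illustration: missingness was made to depend on delivery site alone. That is correct. Step 2 shows the limiting case and step 5 what happens away from it. All the rates are assumed. Section 3.4 links care elsewhere with missing records, but only for women transferred in. Listing outside delivery as a covariate for an mITT analysis may mean that the sponsor expects usable outcomes for such women. The covariate could also be dropped if 1% or more of women lack it, since Section 5.3 says that "if fewer than 1% of subjects have a missing value, that variable will be included as a covariate in the analysis".

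It can also be said that, under the missing-at-random framing of Section 5.10, missingness given covariates is a legitimate question. It is, for the alternative analysis, which adjusts for delivery site. It is not for the primary analysis, which does not.

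Three stronger readings are tempting and should be resisted.
- A reader might infer that this model is the only look at missingness and will tend to report no difference. Section 5.10 also plans missing-data patterns by characteristics and a comparison of the number of missing values, and it sets no rule that a non-significant result means similarity. What it does not explicitly fix is an unadjusted comparison of proportions by arm.
- A reader might infer that NOWS removes lost women from the model. The complete-case rule, "The primary and alternative analyses will use cases with complete data for the included covariates", is not stated for the missingness model, and Section 5.10 names multiple imputation as suitable. The coding of NOWS when no newborn record exists is not given.
- A reader might infer that losses really do differ between the arms. The SAP holds no data on this.

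**Conclusion.** The point holds for delivery site. The plan puts a variable known only at birth, and plausibly a cause of missing neonatal outcomes, into the model meant to compare missingness. As far as excess prospective loss runs through outside delivery, the arm ratio moves toward 1. In the limiting case, crude ratios of about 3 to 8 become 1.0 under the assumed rates; with a further route of loss, some difference remains visible. The result rests on outside delivery being commoner in the prospective arm, on outcomes being missing far more often after it, and on the covariate surviving the Section 5.3 filter.

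NOWS does not belong in this model either, because it is a newborn diagnosis. Any masking through it would need complete-case handling, blank rather than negative coding, and a lack of NOWS concentrated among lost prospective women, so its size cannot be stated.

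Severity is minor. The comparison is a diagnostic, and no effect estimate depends on it.

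**What to change.** Amend SAP Section 5.10 as follows.
1. For each co-primary outcome, report the unadjusted proportion missing by arm in the ITT population, before any mITT or complete-case restriction, with the risk difference or ratio and its 95% CI. Judge similarity from that interval.
2. Limit any adjusted missingness model to variables truly known by the blood draw, leaving out delivery site and NOWS.
3. Fit that model by logistic regression, or by Poisson regression with robust variance.
4. Tabulate losses by place of delivery within arm, so that this route is seen and not adjusted away.

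The cost is one extra table and a change of SAP wording. No new data are needed.

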6.1 Potential bias in the hybrid study

In this study, it is crucial to address selection bias, epoch bias, bias from self-selection of compliant completers in the higher-risk group, as well bias due to COVID-19 / SARS-CoV-2 exposure in the last ~400 subjects. Selection bias is the bias introduced by the selection of individuals, groups or data for analysis in such a way that proper randomization is not achieved, thereby ensuring that the sample obtained is not representative of the population intended to be analyzed. In this study, prospective intervention group and historical cohort study group are not allocated through randomization, therefore selection bias may be one of the important issues to be addressed. As the prospective arm and historical controls received care in different periods, epoch effects from trends in patient care and in public health may also prove an important source of bias. Finally, incomplete acceptance of interventions by some higher risk subjects in the prospective arm provides a source of bias that cannot be directly adjusted, as no higher risk group defined by PreTRM® risk score is present amongst the historical controls. Bias due to comparison of historical controls from a pre-pandemic period to prospective subjects reaching term during the SARS-CoV-2 pandemic has been ameliorated by restriction of the study to subjects reaching term before detection of the first SARS-CoV-2 positive case in Delaware.

Bias from any source will cause the distortion of a statistical analysis. Bias can have varying effects, and the magnitude of its impact and the direction of the effect are often hard to determine. If bias is not taken into account, the results and conclusions of the study may be false or misleading. Therefore, it is necessary to consider the sources of bias in the outcomes analysis.

6.2 Potential differences between historical and prospective cohorts

The assessment of selection bias involves assumptions regarding inclusion or participation by potential subjects, and results can be highly sensitive to assumptions. Even with external validation data, which may work for unmeasured confounders, it is difficult to account for more than a trivial amount of selection bias. Self-selection bias in consenting of higher-risk subjects to interventions further depends on PreTRM® score, a

factor measured only in the prospective arm. Assessment of epoch bias adds assumptions regarding the composition of standard care and incidence of comorbid conditions due to public health trends. Since the study population is a hybrid of prospective cohort and historical cohort, instead of randomized clinical trial, bias is the key issue in the analysis of outcomes. Using appropriate methods to address bias is critical in the study. Different approaches have been applied, including multivariate analysis with covariate adjustment in the studies in which selection bias needs to be handled, and more recently, propensity scoring. Propensity score analysis, includes subgroups defined by propensity score, propensity score used as a covariate in multivariate analysis, matched patients in two groups by propensity score, and inverse probability weighting. Methods based on propensity scores have become important in addressing selection bias in recent years. Other methods are instrumental variable and regression discontinuity design (RDD).

Comparison of diverse adjustment methods as specified in the primary, secondary and exploratory analyses will enable assessment of the degree of selection and epoch bias in the study, and the quality of prespecified and exploratory adjustments for bias.

As well, exploratory analyses within the prospective arm will provide additional estimates of intervention efficacy without reference to historical controls.

Statistical Analysis Plan for AVERT Economic Study (SEAR, Separate Document)

REFERENCES

- 1 Anderson, Robert N, and Betty L Smith. 2003. “Deaths: Leading Causes for 2001.” *National Vital Statistics Reports : From the Centers for Disease Control and Prevention, National Center for Health Statistics, National Vital Statistics System* 52 (9): 1–85. <http://www.ncbi.nlm.nih.gov/pubmed/14626726>.

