Hypothesis: A cohort of pregnancies who are screened using the PreTRM® test around 20 weeks gestation in which a bundle of interventions is given for elevated PreTRM® risk will show either decreased neonatal morbidity/and mortality (measured as a composite score, “NMI”), or decreased length of neonatal stay in the hospital (NNOLOS). Secondarily, they will show an increase in gestational age at birth (GAB) and a reduction in length of neonatal NICU stay (NICULOS), compared to an unscreened historical control group.

Study Design Type: Prospective cohort study of screened pregnant women compared to a historical control.

Population: Prospective subjects are recruited from ChristianaCare’s patient population as described in the study protocol. A comparable control population will be identified from ChristianaCare’s database, as described in the study protocol. A total of approximately 10,000 women meeting the screening protocol will be identified with delivery prior to July 6th, 2018. Women will be sequentially identified retrospectively who qualify for the study based on applicable inclusion and exclusion criteria. As such cohort definition dates can only be estimated but are noted with a delivery of volume of approximately 6,000 deliveries a year, this would approximate a start date for the historical cohort of August 6th, 2016.

Intervention: Qualifying women will be screened using the PreTRM® test (Sera Prognostics, Inc.) at a large tertiary care center. Predicated upon the degree of risk based on a prespecified algorithm that includes height, weight, and measurement of two serum proteins (IBP4 and SHBG), women will be treated according to a pre-determined protocol. The outcomes of the screened cohort of women will be compared to those of the historical control group at the same tertiary care center.

Outcomes:

Co-Primary outcomes: To determine whether a cohort of women who are screened with the PreTRM® test and then managed according to a prespecified protocol will have statistically significant reductions in either (a) composite neonatal morbidity and mortality (NMI score), or (b) length of neonatal hospital stay (NNOLOS), compared to a historical control group.

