- Length of neonatal NICU stay (NICULOS): days from admission to neonatal intensive care (NICU) to neonatal discharge home from the NICU or until death if occurring before discharge. This includes all levels of care designated by ChristianaCare as intensive care, including all transfers across levels of intensive care. Nursery and non-intensive care days are not included. This will be calculated in fractional days if times of admission and discharge are available and rounded to the nearest integer value of total days, or as the number of total days in intensive care if times are not available; times are not required. NICULOS is set to zero for babies never admitted to the NICU but admitted to the hospital. In cases of stillbirth or neonatal mortality in the NICU, NICULOS is set to one day longer than the maximum length of stay recorded for any infant. NICULOS will be truncated at $44^{0/7}$ weeks of gestational age as specified in the protocol.

- Duration of gestation: GAB is set to $40^{0/7}$ weeks for deliveries on the estimated due date (EDD) and adjusted by the difference in days between the date of delivery and the EDD for all other births. The EDD is established by ultrasound data or accurately known last menstrual period (LMP), according to ACOG guidelines, as described in the protocol.

Safety outcomes: monitoring of adverse events is described in the protocol.

4. Determination of Sample Size

This study has been terminated due to the advent of the SARS-CoV-2 pandemic in the ChristianaCare population. At study termination, 1,873 subjects were enrolled in the study. To avoid bias in comparison of pre-pandemic controls to prospective subjects who reached term during the pandemic period, the primary analysis of the study will be limited to an estimated 1,453 subjects who reached $37^{0/7}$ weeks gestation before local spread of SARS-CoV-2 in Delaware and the associated shut-down of non-COVID-19 research at ChristianaCare.. Approximately 10,000 historical controls were selected from a period of about 2 years immediately prior to study initiation.

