5.4 Primary and Alternative Analyses

The primary and alternative analyses will be performed in the modified ITT (mITT) population on the primary, secondary and exploratory endpoints.

The primary analysis is regression with covariates as specified for each endpoint.

The alternative analysis is regression with covariates as specified for each primary, secondary and exploratory endpoint, with weighting by inverse propensity score to address potential selection bias.

Propensity-matched and unadjusted “raw” analyses are pre-specified as exploratory analyses. These analyses will be performed on primary and secondary endpoints.

In analysis combining primary, alternative and exploratory analyses, we will present the demographic and baseline characteristics differing between the prospective arm and historical controls, selected from among the covariates prespecified for the primary and alternative analyses. We will compare the primary analysis using prespecified covariates, the alternative analysis using IPW, and exploratory PSM un-adjusted (raw) data analyses (Table 2). The results from these four distinct methods are expected to show similarity in direction and potentially in magnitude of effect. If differences in direction are observed, further analysis such as double robust propensity score analysis will be conducted.

Variable	Covariate Regression			Inverse Probability Weighted			Matched data			Unadjusted “Raw” data		
	Prospective (N=)	Historical (N=)	p-value	Prospective (N=)	Historical (N=)	p-value	Prospective	Historical	p-value			
Age												
Parity												

Table 2: Baseline Characteristics

For pre-specified analysis populations and for subgroups specified under Subgroup Analyses below, analyses will be conducted to examine the clinically important groups and unbalanced variables between the prospective and historical cohorts.

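### Comparing the planned adjustment methods cannot show epoch bias from drift in care practice, because all four contrast the same two non-overlapping periods

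*SAP*

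**What the plan says.** - **Section 6.1** accepts the problem: "epoch effects from trends in patient care and in public health may also prove an important source of bias".
- **Section 2 (Population)** takes controls "with delivery prior to July 6th, 2018" and adds that "this would approximate a start date for the historical cohort of August 6th, 2016". Section 4 describes them as "selected from a period of about 2 years immediately prior to study initiation".
- **Section 5.4** sets covariate regression, inverse propensity weighting, propensity matching and the unadjusted analysis side by side: "The results from these four distinct methods are expected to show similarity in direction and potentially in magnitude of effect". The only trigger for more work is disagreement in direction: "If differences in direction are observed, further analysis such as double robust propensity score analysis will be conducted".
- **Section 6.2** concludes that comparing adjustment methods across the primary, secondary and exploratory "analyses will enable assessment of the degree of selection and epoch bias in the study". A separate sentence then offers the analyses within the prospective arm as further estimates of efficacy.

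**The concern.** Controls delivered before the study began and prospective women delivered after it began, so arm and calendar period are one variable. A method that compares the arms also compares the periods. If neonatal units changed their admission thresholds or discharge habits between the periods, each of the four estimates would carry that change, and the four could agree closely for that reason alone.

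The endpoints are sensitive to such changes. NNOLOS is a length of stay, and the NMI assigns its levels partly by days in the NICU (section 3.7). A reader who relies on the sentence in section 6.2 could take agreement among the methods as evidence that epoch bias is small, when agreement says nothing about the care-practice part of it.

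**Working it through.** **Inputs from the SAP.** Prospective arm about 1,453 and controls about 10,000; 34% screen positive and 55% compliance among higher-risk women; NMI of 3 or more in 0.036 of controls and 0.023 to 0.020 of the prospective arm (section 4); one-tailed tests (section 5); Holm at 0.05, so 0.025 at the first step (section 5.5); 1,873 enrolled in total.

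**1. The plan's own power.** Removing untreated higher-risk women, as the mITT definition does, gives n = 1,453 × (1 − 0.34 × 0.45) = 1,231. A two-proportion test, 1,231 vs 10,000, one-sided 0.025, has power 0.68 (0.036 vs 0.023) and 0.88 (0.036 vs 0.020). This reproduces the stated 0.7–0.9, so 1,231 is used below.

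**2. What the four methods share.** The propensity model in section 5.3 predicts arm, which is also period. Neither covariate list contains calendar time, and adding it would not separate it from arm. The methods differ only in how they treat measured maternal characteristics.

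**3. Simulation of that point.** Two cohorts (1,231 and 10,000), no treatment effect, a modest case-mix difference, binary NMI of 3 or more, and an assumed period odds ratio (OR); 300 runs each:

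| Assumed period OR | Covariate | IPW | Matched | Raw | All four favour prospective arm |
|---|---|---|---|---|---|
| 0.8 | 0.80 | 0.80 | 0.80 | 0.88 | 76% |
| 0.7 | 0.68 | 0.68 | 0.68 | 0.75 | 92% |

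The three adjusted methods agree and return the period effect as if it were a treatment effect. Raw departs from them only through the measured case mix.

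**4. Possible size.** The drift rates and the gap between periods are assumptions. The control midpoint is about 21 July 2017. Suppose enrolment began in July 2018 and the 1,873 − 1,453 = 420 women not yet at 37 weeks represent about 17 weeks of accrual. That is 420/17 = 24.7 per week, and 1,453/24.7 = 59 weeks. The enrolment midpoint is then about 29 weeks in, and births follow about 19 weeks later, near June 2019: a gap of about 1.9 years. The value 2.2 allows for a later midpoint.

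RR = (1 − d)^gap; p1 = 0.036 × RR; SE² = (1 − p1)/(1,231 p1) + (1 − 0.036)/(10,000 × 0.036); rejection = Φ(−1.96 − ln RR/SE).

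For d = 0.10 and gap 1.9: RR = 0.819, p1 = 0.0295, SE = 0.172, rejection = Φ(−1.96 + 0.200/0.172) = 21%.

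| Assumed yearly fall | RR (gap 1.9 to 2.2) | Rejection at nominal 2.5% |
|---|---|---|
| 3% | 0.94 | about 6% |
| 5% | 0.91 to 0.89 | 9–10% |
| 10% | 0.82 to 0.79 | 21–27% |

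**5. What the controls could show about drift.** Deliveries spread evenly over 1.91 years have SD 1.91/√12 = 0.552 years. The slope SE on the log-odds scale is 1/(√(10,000 × 0.036 × 0.964) × 0.552) = 1/(18.6 × 0.552) = 0.097 per year. A 10% yearly fall is ln 0.9 = −0.105, so z = 1.08 and two-sided power at 0.05 is about 19%; for a 5% fall it is about 8%. Projected forward, the 95% factor around a flat trend is exp(±1.96 × 0.097 × gap): 0.70–1.44 at 1.9 years and 0.66–1.52 at 2.2 years. The smaller planned effect is OR (0.023/0.977)/(0.036/0.964) = 0.63.

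**The case against.** A reader might infer that the SAP ignores epoch bias or has no evidence free of it. The text does not support that. Sections 2, 6.1 and 6.2 disclose the bias and its dependence on assumptions. In section 5.7, the risk-score discontinuity and the comparison of higher-risk with not-higher-risk women use prospective subjects only. Set beside the primary estimate, they bear indirectly on epoch and selection bias combined. This stands. Their limits are that they are exploratory, that the mITT population leaves out higher-risk women who did not start treatment (so self-selection enters), and that no rule covers a conflict with the primary result.

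A reader might also infer that every epoch effect passes whole through all four methods. It does not. Section 6.2 counts trends in comorbid conditions as part of epoch bias, and the propensity lists include chronic hypertension, gestational diabetes, BMI and smoking. Weighting and matching remove some of that part, and comparison with the raw result is informative about it. Section 5.7 also touches aspirin, progesterone and antenatal steroid use.

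Nor are the controls the only untreated data. The not-higher-risk women and the non-intervention completers are untreated and contemporaneous, and section 5.7 sets both beside the controls, although risk selection confounds those comparisons.

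Finally, section 5.4 states an expectation of agreement; it does not say that agreement proves absence of bias. The sentence in section 6.2 governs no test or decision rule.

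**Conclusion.** The concern holds for drift in care practice that the measured covariates do not carry. For that component the section 5.4 comparison is uninformative, and section 6.2 claims too much. It does not extend to the whole of epoch bias, nor to the prospective-only analyses.

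The rejection rates of about 6%, 9–10% and 21–27% rest on assumed drift, an assumed gap of 1.9–2.2 years and a raw two-proportion test at n of about 1,231. The same bias enters each of the four methods, but these exact rates should not be read as applying to each: matching uses at most four controls per subject, and the planned NMI test is a weighted ordinal regression. Non-overlap is by delivery period; the SAP gives no exact enrolment start date.

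One might hope that a trend test in the controls would settle the matter. With about 19% power for a 10% yearly fall, it cannot.

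**What to change.** 1. In section 6.2, limit the sentence to measured confounding, and state that agreement among the section 5.4 methods is not evidence against an epoch effect from trends in care.
2. Add two sensitivity analyses on data already held: the NMI and NNOLOS models fitted in controls by delivery date, reported as a slope with 95% confidence interval; and the primary analysis repeated with controls from the latest 12 months only.
3. State that a non-significant control trend does not exclude epoch bias. Show any projection of the trend as a descriptive sensitivity analysis with its interval, and say in the conclusion that the arm effect cannot be fully separated from calendar period.

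The cost is a change of wording and a few more model runs. The trend interval will be wide and the conclusion more cautious.
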